5.5.6 Rescue medication

Rescue medication is defined as medication used to control symptoms that are not adequately controlled on investigational and other study treatment.

Use of rescue medication is prohibited. Please see [Section 5.5.7](#) and [Section 5.5.8](#) for details on concomitant medications. Although no subject will be restricted from receiving necessary rescue medications for lack of benefit or worsening of disease, subjects will be discontinued from the study if treated with prohibited medications (as described in [Section 5.5.8](#)) and should complete an Early termination visit at the earliest possible time-point and enter the Post-treatment follow-up period. Efficacy and safety will be assessed in detail at every study visit and, subjects who are deemed by the Investigator not to be benefiting from study treatment, or for any reason on the subject's own accord, will be free to discontinue study participation at any time.

Use of rescue medication must be recorded on the corresponding eCRF page.

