5.5.8 Prohibited medication

Use of the treatments displayed in [Table 5-1](#) is NOT allowed after screening due to their confounding effect and/or safety interactions.

Note: Live vaccination is NOT allowed within 6 weeks before baseline and until after 3 months following the last study dose. Killed or inactivated vaccines may be permitted according to the investigator's discretion.

It is recommended not to initiate biologic treatment until 3 months after the last dose of study drug. Therefore, biologic treatment should not be used any time during study participation.

Table 5-1 Prohibited medication

Medication	Prohibition period / washout before baseline	Action taken
Any biologic drugs, including but not limited to TNF α inhibitors, secukinumab, or other biologic drug directly targeting IL-17 or IL-17 receptor, any biological DMARD (bDMARDs)	Previous exposure at any time: exclusion criterion	Discontinue investigational treatment
Any cell-depleting therapies including but not limited to anti-CD20 or investigational agents [e.g., alemtuzumab (Campath), anti-CD4, anti-CD5, anti-CD3, and anti-CD19].	Previous exposure at any time: exclusion criterion	Discontinue investigational treatment
Conventional DMARDs (except SSZ (for ERA only) or MTX)	4 weeks	Discontinue investigational treatment

Medication	Prohibition period / washout before baseline	Action taken
including apremilast		
Leflunomide	8 weeks	Discontinue investigational treatment
Leflunomide with cholestyramine washout	4 weeks	Discontinue investigational treatment
Any investigational treatment or participation in any interventional trial	4 weeks, or until the expected pharmacodynamics effect has returned to baseline or 5 half-lives (whichever is longer)	Discontinue investigational treatment
Analgesics other than NSAIDs, paracetamol/acetaminophen, and low strength opioids PRN	2 weeks	

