Systemic corticosteroids at a prednisone equivalent dose of ≤ 0.2 mg/kg/day or up to 10 mg/day maximum, whichever is less, is permitted if the dose is stable at least 7 days before baseline. *Corticosteroid dose can be tapered down to discontinuation in Treatment Period 2 for patients with 3 consecutive months of minimum ACR50 response or at any time in Treatment Period 3 based on investigator judgment. No changes in corticosteroid dose will be allowed in Treatment Period 1.	1 week	If administered due to a medical urgency unrelated to the patient's arthritis, study treatment should be interrupted until the steroid is discontinued – if not medical urgency or if related to the patient's arthritis, then discontinue from the study may be required on a case by case basis.
Intra-articular corticosteroids are not permitted within 4 weeks prior to baseline or at any time in Treatment Period 1 or 2. Intra-articular corticosteroid injections will be permitted in Treatment Period 3 but no more than 4 joints per 24-week period may be injected and no single injection should exceed 40 mg of triamcinolone (or equivalent) during any 52-week period. The joints injected with intra-articular corticosteroids will be assessed as both swollen and tender in the SJC and TJC, from injection time onwards.	4 weeks	Discontinue investigational treatment, (see Section 5.5.7)
Intramuscular or intravenous corticosteroid treatment are not permitted	4 weeks	Discontinue investigational treatment or from study may be required on a case

Medication	Prohibition period / washout before baseline	Action taken
		by case basis.
Live vaccinations	6 weeks	Discontinue investigational treatment for 12 weeks and patient should remain in the study and follow visit schedule.
Oral or topical retinoids	4 weeks	Discontinue investigational treatment
Photochemotherapy (e.g. PUVA)	4 weeks	Discontinue investigational treatment
Phototherapy (UVA or UVB)	2 weeks	Discontinue investigational treatment
Topical skin treatments (except in face, eyes, scalp and genital area during screening period only, and if topical corticosteroids, only those with mild to moderate potency)	2 weeks	Discontinue investigational treatment may be required on a case by case basis.

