5.6.2 Discontinuation of study treatment

The Investigator must discontinue study treatment for a given patient if, on balance, he/she believes that continuation would negatively impact the risk/benefit of trial participation.

Study treatment must be discontinued under the following circumstances:

- Patient/Guardian wish /withdrawal of informed consent
- Pregnancy (see [Section 6.5.7](#) and [Section 7.6](#))
- Use of prohibited treatment as per recommendations in [Table 5-1](#)
- Any situation in which study participation might result in a safety risk to the patient
- Emergence of the following adverse events:
 - Any severe or serious AE that is not compatible with administration of study medication, including AEs that require treatment with an unacceptable co-medication
 - Onset of lymphoproliferative disease or any malignancy except for treated basal cell carcinoma, treated actinic keratoses, treated in situ carcinoma of the cervix or non-invasive malignant colon polyps which are being or have been removed
 - Life-threatening infection
 - Severe hypersensitivity reaction or anaphylactic reaction
- Any laboratory abnormalities that in the judgment of the Investigator are clinically significant and are deemed to place the subject at a safety risk for continuation in the study (A general guidance on clinically notable laboratory values is provided in [Appendix 1](#)).
- Use of any biologic immunomodulating agent except secukinumab
- Any protocol deviation that results in a significant risk to the subject's safety.

If permanent discontinuation of study treatment prior to Week 100 occurs, the patient should NOT be considered withdrawn from the study. The patient should return to the clinic 4 weeks after last study drug administration, for a premature discontinuation visit and 12 weeks after “last study drug administration” for a Post-treatment follow-up visit. Assessments performed at these two visits are detailed in the “premature discontinuation visit” and “Post-treatment follow-up visit” respectively in [Table 6-1](#) and should be completed and recorded in the appropriate eCRF page. The Investigator must determine the primary reason for the patient’s premature discontinuation of study and record this information on the Dosage Administration eCRF page and also contact the IRT to register the patient’s discontinuation from study treatment.

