9.4 Analysis of the primary variable(s)

9.4.1 Variable(s)

The primary efficacy endpoint will be time to disease flare event in Treatment Period 2, which is defined as the interval between the date of randomization to the date of first occurrence of disease flare event. The analysis of the primary efficacy endpoint will be based on the FAS Treatment Period 2.

All subjects who enter Treatment Period 2 will be followed until the sooner of either experiencing a disease flare or the end of Treatment Period 2 when 33 flare events are observed. Subjects who have not experienced flare event at the end of Treatment Period 2 data (as defined in [Section 3.1](#)) or discontinue prematurely from Treatment Period 2 before it closes for reasons other than experiencing a disease flare will be censored at the date of the last efficacy evaluation in Treatment Period 2.

Statistical model, hypothesis, and method of analysis

The primary objective for Treatment Period 2 of the study is to show superiority of secukinumab over placebo regarding the primary variable in Treatment Period 2.

The following statistical hypothesis will be tested once the required number of flares has been observed and the study has been stopped:

$$H_0: 1 - S_{AIN}(t) \geq 1 - S_{Pla}(t)$$

$$H_A: 1 - S_{AIN}(t) < 1 - S_{Pla}(t)$$

at each time point t , with $S_{AIN}(t)$ and $S_{Pla}(t)$ being the survivor functions in the secukinumab and placebo treatment group at time t .

The two treatment groups will be compared using a one-sided stratified Logrank test with the stratification factor of JIA category (ERA or JPsA) at the 2.5% level of significance. Hazard ratios and their associated 95% confidence intervals will be estimated based on a Cox proportional hazards model with treatment and stratification factor as explanatory variables.

The Kaplan-Meier estimates of the proportion of patients with the flare event at selected landmark points, along with its 95% confidence intervals using Greenwood's formula, will be provided. The primary analysis will be based on the FAS for Treatment Period 2.

Handling of missing values/censoring/discontinuations

All patients in Treatment Period 2 will have a value of time to flare either by having an event or being censored.

Supportive analyses

For sensitivity purposes, the primary analysis will be repeated using an unstratified log-rank test.

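### Section 5.5.6 and Table 5-1 give different rules for steroid rescue in Treatment Period 2, and the supportive analysis, keyed to leaving the study, misses steroid-treated patients who are kept on study drug

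*Protocol*

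**What the plan says.** **Conduct.** Section 5.5.6 (Rescue medication) does not withhold necessary rescue, but states without exception that "subjects will be discontinued from the study if treated with prohibited medications", and defines those medications by reference to Section 5.5.8. Table 5-1 in Section 5.5.8 sets the action row by row:

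- Systemic corticosteroid, when not a medical urgency or when given for the arthritis: "if related to the patient's arthritis, then discontinue from the study may be required on a case by case basis".
- Intramuscular or intravenous corticosteroid, whatever the reason: "Discontinue investigational treatment or from study may be required on a case" (the phrase is completed over the page break as a case-by-case basis).
- Intra-articular corticosteroid: "Discontinue investigational treatment, (see Section 5.5.7"). The row headed "Conventional DMARDs (except SSZ (for ERA only) or MTX") also stops study drug. Neither row removes the patient from the study.
- Live vaccination: study drug is paused for 12 weeks and the patient stays in the study.

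Section 5.6.2 lists, among the reasons to stop study treatment, "Use of prohibited treatment as per recommendations in" Table 5-1. It adds that after permanent discontinuation of study treatment before Week 100 "the patient should NOT be considered withdrawn from the study".

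**Analysis.** In Section 9.4.1 the primary analysis follows patients to flare or to the closure of Treatment Period 2. Those who "discontinue prematurely from Treatment Period 2 before it closes for reasons other than experiencing a disease flare will be censored" at the last efficacy evaluation in that period. One supportive analysis repeats the primary analysis and counts a flare, at the time of leaving, for patients who leave the study for any reason.

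**The concern.** The same patient can be handled in two ways. A site that follows Section 5.5.6 removes a child given prednisone for worsening arthritis, and the primary analysis censors that child. A site that follows Table 5-1 may keep the child on blinded drug, at risk, with later flare assessments made under steroid. Flare needs worsening of at least 30% in at least three of six components (Appendix 8). These include joint counts, global assessments and CRP, which steroid can improve, so a flare may be delayed or missed.

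Need for anti-arthritic rescue lies close to the outcome being measured. A supportive analysis that treats early exit as failure is the natural place to test it, but the stated trigger does not match the primary censoring rule. The primary analysis censors on leaving Treatment Period 2; the supportive analysis acts on leaving the study. Retained steroid-treated patients are outside it. For patients who stop study drug, the wording in Section 5.6.2 leaves open whether they are inside it.

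**Working it through.** **1. The texts side by side.** For a Treatment Period 2 patient without flare who receives prohibited treatment for the arthritis:

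| Route | Source | Primary analysis | Supportive analysis |
|---|---|---|---|
| Removed from study | 5.5.6 | Censored | Flare |
| Study drug stopped, not withdrawn | Table 5-1 fixed rows; 5.6.2 | Censored | Unclear |
| Kept on study drug | Table 5-1 steroid rows | At risk; later flare counts if criteria are met | Same as primary |

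Section 5.6.2 defers to Table 5-1, so it adds no third rule and does not settle the first two.

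**2. The plan's own figure.** Inputs from Sections 5.3 and 9.6: hazard ratio (HR) 0.32, 33 flares, one-sided 0.025, 90% power, 1:1 allocation. Schoenfeld events = 4(1.960 + 1.282)² / (ln 0.32)² = 42.0 / 1.298 = 32.4, rounded up to 33. Power with 33 events = Φ(√33/2 × |ln 0.32| − 1.96) = Φ(3.273 − 1.96) = 90.5%. The plan's figure reproduces.

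**3. Effect of one affected placebo patient.** The protocol gives neither a rescue rate nor a placebo median, so this is for scale only. Simulation assumptions: 60 patients with placebo median 4 or 7 months, or 80 patients with 7 or 10 months (medians assumed); exponential times rounded up to 4-weekly visits; 12-month accrual; at most 21 months in Treatment Period 2; stop at the 33rd flare; two equal strata; stratified one-sided log-rank test at 2.5%; HR = exp((O − E)/V). There were 5000 trials per scenario, with the same random numbers across variants. The Monte Carlo standard error of each power is about 0.5 points.

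| N / placebo median | No masking: power, median HR | One flare delayed 12 weeks | One flare never counted |
|---|---|---|---|
| 60 / 4 months | 87.7%, 0.306 | 86.7%, 0.311 | 84.3%, 0.330 |
| 60 / 7 months | 88.9%, 0.313 | 88.1%, 0.317 | 84.9%, 0.338 |
| 80 / 7 months | 88.2%, 0.321 | 87.5%, 0.324 | 86.1%, 0.334 |
| 80 / 10 months | 88.2%, 0.323 | 87.8%, 0.326 | 85.3%, 0.341 |

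By subtraction, a delay costs 0.4 to 1.0 points of power and moves the HR by +0.003 to +0.005. A flare never counted costs 2.1 to 4.0 points and moves the HR by +0.013 to +0.025. Repeat runs of the same scenarios widen the power ranges to 0.4 to 1.1 and 2.1 to 4.8 points.

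**4. The alternative of stopping study drug.** If that patient is instead taken off drug and censored before the flare, the loss in repeat runs is 1.2 to 1.9 points per patient: more than for a delayed flare, less than for one never counted.

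**5. Several patients.** With 35 per arm, an assumed placebo median of 6 months, and 10% of placebo patients (3.5 patients) masked permanently, power falls from 88% to 76%, or (88 − 76)/3.5 = 3.4 points each. The 10% is an assumption and permanent masking is the upper bound.

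**The case against.** The strongest reply is that Table 5-1 governs and Section 5.5.6 is a loose summary of it. Section 5.5.6 defines its prohibited medications through Section 5.5.8, Section 5.6.2 also points to the table, and several rows stop drug only. This stands as a guide to the repair: the discretion in the table can stay and the sentence in Section 5.5.6 should yield. It does not remove the contradiction, because that sentence is unconditional.

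Second, keeping rescued patients at risk and scoring their observed flares is a legitimate strategy that fits the intention-to-treat approach. This also stands, and is why the primary analysis should not change. A reader might infer that the protocol should require study drug to be stopped after any arthritis-related steroid. The documents do not support that. A retained patient keeps 4-weekly assessments and a later flare still counts. A patient taken off drug is seen at only two further visits, 4 and 12 weeks after the last dose, and is censored for a reason related to the outcome.

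Third, sensitivity definitions often sit in the statistical analysis plan, and the doubt about patients who stop treatment is one of terminology: Section 5.6.2 also speaks of recording the reason for early study discontinuation, and Section 6 gives early leavers the same two visits. That lessens the weight. But the trigger is written in the protocol and does not match the primary censoring rule beside it, and a statistical analysis plan cannot reconcile two conduct rules.

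Fourth, rescue is largely pre-empted. A suspected flare can be assessed at an unscheduled visit, is derived centrally the same day, and if confirmed brings open-label secukinumab at once. This is accepted; the rate is probably low.

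**Conclusion.** The point holds as a correction worth making, not as a threat to the trial. Section 5.5.6 contradicts Table 5-1, and the supportive analysis misses retained steroid-treated patients and is ambiguous for those who stop study treatment.

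The size rests on an unknown rescue rate, assumed placebo medians and the planned HR of 0.32. Per affected placebo patient, the loss of power is about 1 point or less for a 12-week delay and 2.1 to 4.8 points as an upper bound.

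A reader might infer that the primary result could be biased in favour of secukinumab, or its type I error inflated. The documents do not support this. If rescue is commoner on placebo, masked flares are mainly placebo flares and the HR moves towards 1. With no drug effect and the blind intact, there is no reason for rescue to differ by arm. Nor do the documents show that steroid hides flares permanently: flare is derived centrally and counts whenever the criteria are met.

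**What to change.** (a) In Section 5.5.6, replace the statement that such patients leave the study with: *will be handled as specified in Table 5-1*. One rule then governs, and the case-by-case discretion in the steroid rows stays.

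(b) In Section 9.4.1, reword the supportive analysis to count as a flare, at the date it occurs:

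- any premature discontinuation of the study, of study treatment or of Treatment Period 2, for reasons other than closure of that period or reaching Week 104; and
- any arthritis-related prohibited rescue in Treatment Period 2: systemic steroid started or raised above the Week 12 dose, intramuscular, intravenous or intra-articular steroid, or a prohibited DMARD. A return to the Week 12 dose after a permitted taper is not counted.

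The primary analysis, its censoring rule and the 33-flare stop are unchanged; flares counted only in the supportive analysis do not contribute to the 33.

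The cost is one sentence in each of two sections. No new data are needed, because rescue use, concomitant medication and oral steroid dose changes are already recorded (Sections 5.5.6 and 5.5.7). The one added task is a blinded review before database lock of whether each rescue was for the arthritis. Collecting the six flare components before the first rescue dose, where feasible, is good practice but optional and not part of this fix.

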Treatment with oral corticosteroids \leq 0.2 mg/kg/day (or maximum 10 mg/day whichever is lower) of oral prednisone (or equivalent) is permitted if the dose was stable at least 7 days preceding Baseline visit and remains stable. Otherwise a washout period of 1 week prior to Baseline is needed.

Corticosteroids can be tapered down to discontinuation beginning in Treatment Period 2 based on investigator clinical judgment for patients with at least 3 consecutive months of minimum

ACR50 response and at any time in Treatment Period 3 based on investigator clinical judgment. No corticosteroid dose tapering will be allowed in Treatment Period 1.

Any change in the dose of oral corticosteroids during the trial should be recorded on the corresponding eCRF page.

Intra-articular corticosteroid injections are not permitted within 4 weeks prior to Baseline or at any time in Treatment Period 1 or 2. Intra-articular corticosteroid injections will be permitted in Treatment Period 3. No more than 4 joints per 24-week period may be injected and no single injection should exceed 40 mg of triamcinolone (or equivalent) during any 52-week period.

Non-steroidal anti-inflammatory drugs (NSAIDs) (including selective COX-2 inhibitors), low strength opioids and acetaminophen/paracetamol

Subjects are permitted to enter the trial using regular dose of a single NSAID for their arthritis. The dose must be stable for at least 1 week before the baseline visit and remain at this dose during the trial. Other NSAIDs, low strength opioids, and paracetamol/acetaminophen are permitted during the trial only if used on an as required (PRN) basis for non-arthritis treatment. In such cases, the subject must refrain from intake of the PRN medication during at least 24 hours before a visit with a disease activity assessment.

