6.4.1 JIA ACR response criteria

Standard ACR paediatric Criteria (JIA ACR criteria) consist of 6 core components which will be assessed as scheduled in [Table 6-1](#). JIA ACR 30/50/70/90/100 are defined as 30%, 50%, 70%, 90% and 100% improvement from baseline respectively in a minimum of three variables in the core set with no more than one variable worsening more than 30% as defined in the ACR criteria.

The 6 core set variables are summarized below:

- Physician global assessment of disease activity on a 0 - 100 mm VAS from 0 mm = no disease activity to 100 mm = very severe disease activity
- Parent or patient's (if appropriate in age) Global Assessment of Subject's overall well-being on a 0-100 mm VAS from 0 mm = very well to 100 mm = very poor.
- Functional ability: Childhood Health Assessment Questionnaire (CHAQ[©])
- Number of active joints using the ACR definition (any joint with swelling or in the absence of swelling, limitation of motion accompanied by either pain on motion or tenderness not due to deformity)
- Number of joints with limited range of motion
- Laboratory measure of inflammation: CRP (mg/L)

The respective response variables listed above will be used by a central vendor to determine ACR Pediatric response, responder status at Week 12, and flare occurrence in Treatment Period 2. These results will be communicated to the investigator prior to the patient leaving the study site. Additionally, these components will be used to determine JADAS and inactive disease status (Wallace et al. 2011) as part of secondary [REDACTED] analyses.

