6.4.6 Joint counts with limitation of motion

A total of 69 joints will be assessed for limitation of motion at each scheduled visit for all patients throughout the study. The same 75 joints assessed for tenderness ([Section 6.4.8](#)) will also be assessed for limitation of motion excluding the 2 sternoclavicular, 2 acromioclavicular joints as well as the 2 sacroiliac joints.

For there to be consistency between the joint assessments, it is strongly recommended that the same evaluator perform these assessments at all visits.

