6.4.8 Tender and Swollen Joint Count

Tender 75 joint count (TJC)

The following 75 joints will be scored as either tender or not tender:

- Temporomandibular joints: 2
- Sternoclavicular joints: 2
- Acromioclavicular joints: 2
- Shoulders: 2
- Elbows: 2
- Wrists: 2
- Hands:
 - distal interphalangeal
 - 10 proximal interphalangeal
 - 10 metacarpophalangeal
- Hip: 2

- Knee: 2
- Ankle: 2
- Subtalar joints: 2
- Intertarsal joints: 2
- Feet:
 - 10 metatarsophalangeal joints
 - 10 toes
- Cervical spine is assessed as a single joint
- Thoracic spine is assessed as a single joint
- Lumbar spine is assessed as a single joint
- Sacroiliac joints: 2

Joint tenderness is to be scored as present or absent. For there to be consistency between the joint assessments, it is strongly recommended that the same evaluator perform these assessments at all visits.

Swollen joint count (SJC)

A total of 68 joints are to be scored as either swollen or not swollen. The same 75 joints assessed for tenderness will also be assessed for swelling excluding the cervical spine, thoracic spine, lumbar spine, 2 hips and 2 sacroiliac joints.

For there to be consistency between the joint assessments, it is strongly recommended that the same evaluator perform these assessments at all visits.

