9.4.2 Efficacy variables

[figure not shown]
The analysis of secondary variables is descriptive only for FAS. Summary statistics will be presented. Summary statistics for continuous variables include N, mean, standard deviation, minimum, median, maximum, 25% and 75% quantiles, and number of patients with non-missing data. For binary or discrete variables the number of subjects in each category and relative frequencies will be provided.

The following secondary efficacy endpoints will be analyzed for all patients and each JIA category by descriptive statistics in Treatment Period 1:

- JIA ACR 30/50/70/90/100 and inactive disease status
- Each JIA ACR core component
- Change from baseline Juvenile Arthritis Disease Activity Score (JADAS) score
- Total enthesitis count
- Total dactylitis count

The following secondary efficacy endpoints will be analyzed for all patients and each JIA category by descriptive statistics in Treatment Period 2, and/or other periods, as appropriate:

- JIA ACR 30/50/70/90/100 and inactive disease status

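### The scoring rule for steroid-injected joints in Treatment Period 3 covers the swollen and tender counts only, leaving the limited-motion count, and for hips the active joint count, uncorrected

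*Protocol*

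**What the plan says.** Section 5.5.7 bars intra-articular steroid in Treatment Periods 1 and 2 and then states: "Intra-articular corticosteroid injections will be permitted in Treatment Period 3". The limit is: "No more than 4 joints per 24-week period may be injected". The only instruction on scoring an injected joint is in Table 5-1 (Section 5.5.8): "The joints injected with intra-articular corticosteroids will be assessed as both swollen and tender in the SJC and TJC, from injection time onwards".

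Section 6.4.1 lists six JIA ACR core variables. The two joint variables are the number of active joints and "Number of joints with limited range of motion". Under Section 6.4.5 a joint is active if it is swollen or, when not swollen, if its motion is limited and it is also painful on motion or tender.

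Section 6.4.8 takes the swollen count from the 75 tender-count joints, "excluding the cervical spine, thoracic spine, lumbar spine, 2 hips and 2 sacroiliac joints". On limited motion, Section 6.4.6 says: "A total of 69 joints will be assessed for limitation of motion at each scheduled visit for all patients throughout the study". That list is the same 75 joints "excluding the 2 sternoclavicular, 2 acromioclavicular joints as well as the 2 sacroiliac joints", so it includes the hips. The section has no rule for injected joints.

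Section 9.4.2 has JIA ACR response and inactive disease analysed "by descriptive statistics in Treatment Period 2, and/or other periods, as appropriate".

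**The concern.** The natural reading of the Table 5-1 sentence is that a joint treated with local steroid should not afterwards count as improved. The sentence acts on the swollen and tender counts, which the response criteria do not use directly. Its effect on the endpoints depends on whether imputed swelling carries through to the active joint count. It does so for joints on the swollen list. It cannot for hips, which have no swelling score, and it never reaches the limited-motion count.

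The same injection is therefore scored differently in a knee and in a hip, and one of the six core components (two for hips) can improve because of a local steroid. Hips are not a remote case in this population: Section 1.1 describes aggressive arthritis in ERA, with hip replacement more frequent than in adult ankylosing spondylitis. What is at stake is the interpretation of open-label, single-arm Period 3 summaries, where no control group would reveal the effect. Patients who flare in Period 2 also enter that period.

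**Working it through.** **Joint lists (Sections 6.4.5, 6.4.6, 6.4.8).** The number of distal interphalangeal joints is not legible; 8 is assumed, as the stated total of 75 requires.

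- Tender: 75.
- Swollen: 75 − 3 spine − 2 hips − 2 sacroiliac = 68.
- Limited motion: 75 − 2 sternoclavicular − 2 acromioclavicular − 2 sacroiliac = 69.
- Active (on the swollen or the limited-motion list): 75 − 2 sacroiliac = 73.

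All four match the protocol's figures. The joints that can be active only through limited motion number 73 − 68 = 5: two hips and three spine segments.

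**Reach of the Table 5-1 rule, read literally**

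| Component | Joints | Held by the rule |
|---|---|---|
| Active joint count | 73 | 68, through imputed swelling |
| Limited-motion count | 69 | 0 |

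An injected hip is imputed tender, so it stays active only while limited motion is actually observed.

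**Possible effect on the limited-motion component.** Assume that all n injected joints were limited at baseline and still limited when injected, that injection restores their motion, and that no other joint changes. The improvement is n/b for a baseline count b, so a threshold x is met when b ≤ floor(n/x).

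| Injected joints n | Threshold x | n/x | Largest b |
|---|---|---|---|
| 1 | 30% | 3.33 | 3 |
| 4 | 30% | 13.33 | 13 |
| 4 | 50% | 8 | 8 |
| 4 | 70% | 5.71 | 5 |

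With n = 4, b is at least 4. These figures use a single 24-week allowance.

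**Possible effect on the active count, both hips cleared.** The improvement is 2/b: 67%, 50%, 40% and 33% for baseline active counts of 3, 4, 5 and 6. Three is the entry minimum; the other baseline counts are assumptions.

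**Illustrative record.** Baseline: 4 active and 4 limited joints. Two are injected and regain motion; the other two are unchanged.

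| Joints injected | Scoring | Active | Limited |
|---|---|---|---|
| Two hips | Literal rule | 2 (50% better) | 2 (50% better) |
| Two hips | Injected joints carried | 4 (0%) | 4 (0%) |
| Knee and ankle | Literal rule | 4 (0%) | 2 (50% better) |
| Knee and ankle | Injected joints carried | 4 (0%) | 4 (0%) |

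In the hip record the injections supply two of the three components needed for ACR50. A third must still come from elsewhere, so the record alone does not show a false responder.

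**The case against.** The strongest reply is that Section 9 leaves detail to the statistical analysis plan, and that a note in a medication table need not settle every derivation. Period 3 is open-label, Table 2-1 ties no secondary efficacy objective to it, and Section 4 lets investigators adjust background therapy in that period, so attribution to secukinumab alone is already weak. This limits the importance of the point but does not remove it. The protocol does not leave the matter open: it fixes a rule, and that rule does not fit its own joint lists and core components.

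Three stronger readings are tempting, and the protocol does not support them.

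- A reader might infer that the error always favours secukinumab. It does not. For the 68 swollen-list joints the rule holds an injected joint active with no end date. That joint blocks inactive disease for the rest of the study, and a joint not active at baseline is added as a lasting worsening. The net direction across components is not established.
- A reader might extend the point to JADAS in Period 3. Section 9.4.2 lists JADAS for Treatment Period 1 only, when injections are barred.
- A reader might read the baseline ranges above as expected effects. They are upper-end cases. How often injections occur and how often motion returns are not given, and for joints other than hips and spine only one of six components is affected.

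**Conclusion.** The point holds as a gap in a fixed scoring rule. Taken literally, Table 5-1 protects 68 of 73 joints in the active count and none of 69 in the limited-motion count. Descriptive Period 3 JIA ACR summaries can credit an injection's effect on limited motion, and for hips also its effect on the active count and on inactive disease.

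The possible size rests on injected joints regaining motion and on small baseline counts, and its frequency cannot be estimated from the protocol. The primary time-to-flare analysis and all Period 1 and 2 results are unaffected, because injections are not permitted there. This is a low-cost improvement and no threat to the trial's main conclusion.

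**What to change.** Extend the Table 5-1 scoring sentence along these lines: from the injection onwards, an injected joint is counted as active in the active joint count, including joints not assessed for swelling such as the hips, and as limited in motion if it was limited at the last assessment before the injection; these values are used for JIA ACR response and inactive disease status in Period 3. The rule applies within the existing 73-joint and 69-joint lists, so sacroiliac joints remain outside both.

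Use the last status before the injection, not baseline status. A joint that was limited at baseline but had regained motion on secukinumab before being injected would otherwise lose a genuine benefit.

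The cost is one sentence and a small change to the central derivation and the analysis programs, with no new data. The drawback is that Period 3 response rates become slightly less favourable.
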